6.1.2 Additional Descriptive Data Analyses

1. CardioMEMS™ PA pressure data during LVAD speed ramp test, when done as standard of care, will be summarized over 6 months.

This confidential document is the property of Abbott and shall not be reproduced, distributed, disclosed or used without the express written consent of Abbott.

2. CardioMEMS PA pressure data during collection of right heart catheterization (RHC) data, when done as standard of care, will be summarized over 6 months.
3. LVAD speed, power, and estimated flow parameters will be summarized over 6 months.
4. Heart Failure medications will be summarized as both counts and total daily dosage according to class of medication at baseline 1, 3, and 6 months.

6.1.3 Adverse Events

All protocol-required adverse events (AE) will be summarized by type of AE (non-serious AE, serious AE, non-serious device-related AE and serious device-related AE) at 1, 3, and 6 months.

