5.5.2 Scheduled Follow-ups

Follow-up schedules are calculated from the time of baseline. Follow-up visits are scheduled at Months 1, 3, and 6 post study enrollment (two devices implanted). Sponsor Representatives will be involved in providing technical support during the Follow-up procedures.

At each visit, the following procedures must be completed:

- Document all changes in cardiovascular medications: ACE inhibitors, ARBs, beta blockers, nitrates, aldosterone antagonists, digoxin and diuretics
- Record vital signs
- NYHA Classification
- Administer EQ 5D 5L survey
- Review and document changes in pump parameters
- Administer 6MHW test per Appendix D
- CardioMEMS PA readings taken before (at rest) 6MHW test and immediately following 6MHW test, ideally within one minute of test completion (Group A and Group B)
- Emergency room visits, hospitalizations and cause for hospitalization documented
- Occurrence of protocol defined AEs (date of adverse event, determination of the seriousness and/or relation to the device, resolution of the adverse event)
- Reoperations/operative procedures pertaining to the two devices under study (HeartMate and, CardioMEMS)
- Pump Replacements/Explants/Device Exchanges (note patients are required to be withdrawn from the study at the time either device is removed)

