8.2 SAFETY REPORTING

Safety surveillance within this study and the safety reporting performed both by the investigator and Sponsor for these market release devices starts after the indicated devices have been implanted and as soon as the subject is enrolled in this clinical investigation (refer to section 5.4 for enrollment timing). Procedure related adverse events, prior to both devices being successfully implanted, do not require reporting within this study.

The safety surveillance and the safety reporting will continue until the last investigational visit (six months) has been performed, the subject is deceased, the subject/investigator concludes his participation into the clinical investigation or the subject withdrawal from the clinical investigation.

For purposes of this study, any adverse event that is possibly or likely related to either device, will be collected throughout the clinical investigation. Refer to device specific user manuals. Additionally, adverse events that are possibly or likely related to treating to target ranges (detailed below) will be reported to the Sponsor on a CRF.

Adverse events will be monitored until they are adequately resolved or the subject has ended his/her participation in the trial, whichever comes first. The status of the subject's condition should be documented at each visit.

For the purposes of this clinical investigation, the following events that could be potentially caused by using the CardioMEMS™ device to manage PA pressures to target ranges in patients with HeartMate™ Left Assist devices require reporting. The following adverse events will be required to be reported within the study if they are possibly or likely related to the study procedures or to either of the study devices (see Appendix B for definitions):

- Cardiac Arrhythmias
 - Ventricular Arrhythmia
 - Supraventricular Arrhythmia
 - Both (Ventricular and Supraventricular Arrhythmia)
- Strokes regardless of their types and etiology
 - Hemorrhagic Stroke
 - Ischemic Stroke
 - Debilitating Stroke
- Other Neurological Events felt to be related to managing PA pressures
- Renal Dysfunction secondary to heart failure
- Respiratory Failure secondary to cardiovascular cause
- Right Heart Failure
- Syncope/presyncope/dizziness and hypovolemia
- Worsening Heart Failure
- Other Adverse Event that in the opinion of the investigator are suspected to be related to using the CardioMEMS device to manage PA pressures to target ranges.

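### Harms of managing PA pressure to target are to be collected, but the planned adverse-event summary does not show them by event type or by relation to that management

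*Combined protocol and SAP*

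**What the plan says.** Section 8.2 asks for two streams of adverse events. One is anything possibly or likely related to either device. The other concerns the strategy: "adverse events that are possibly or likely related to treating to target ranges (detailed below) will be reported to the Sponsor on a CRF". The list that follows is introduced as "events that could be potentially caused by using the CardioMEMS™ device to manage PA pressures to target ranges". It has nine top-level items: arrhythmia, stroke, other neurological events, renal dysfunction, respiratory failure, right heart failure, syncope/presyncope/dizziness with hypovolemia, worsening heart failure, and a catch-all for other events. The sentence that makes the list reportable then sets a different condition: "if they are possibly or likely related to the study procedures or to either of the study devices".

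For scheduled visits, section 5.5.2 describes what is taken down for each event: "Occurrence of protocol defined AEs (date of adverse event, determination of the seriousness and/or relation to the device, resolution of the adverse event".

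Section 6.1.3 is one sentence. Protocol-required events are to be "summarized by type of AE (non-serious AE, serious AE, non-serious device-related AE and serious device-related AE) at 1, 3, and 6 months". No other adverse-event analysis is specified.

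**The concern.** The intervention of interest is the practice of steering PA diastolic pressure into a range by changing drugs or pump speed. Neither piece of hardware is itself the question. The likely harms of that practice, such as hypovolemia, syncope or renal dysfunction, come from the treatment changes. Section 8.2 recognises this in the way its list is introduced, but the analysis returns to a device-safety layout.

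The study is meant to shape treatment strategies and later trials. A designer of the next trial would want to know how many patients had syncope or hypovolemia, renal dysfunction or right heart failure, and how many of those events were put down to guided management. The planned table gives neither count. A low device-related count could also be read as reassurance about the strategy, which it would not provide.

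**Working it through.** The point is textual, and the plan states no figure to reproduce. The check follows one kind of event through the plan: syncope after a diuretic change made to reach the target range.

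**Step 1: is it reportable?** Under the first sentence of 8.2 (treating to target), yes. Under the second (study procedures or either device), it is reportable only if the site regards guided management as a study procedure or as a matter of the device. Guided management is described in section 5.6, within the Procedures section, so the first option is arguable. The plan does not say so.

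**Step 2: what is recorded?** The category is recorded, because 8.2 lists it. Attribution to guided management is not among the attributes named in 5.5.2. Only the catch-all item ("suspected to be related to using the CardioMEMS device to manage PA pressures to target ranges") and the item for other neurological events carry it in their own wording. A named category such as syncope does not.

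**Step 3: which row of 6.1.3 does it enter?** Appendix B ties a device effect to use of the study device and does not say whether treatment guided by the sensor is such use. Either answer is open to an investigator.

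**Step 4: what does the reader of the table see?** Assume, for illustration only, 15 syncope/hypovolemia events from guided management and 2 events from a device.

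| Site's reading | Device-related rows | All reported events |
|---|---|---|
| Guided treatment is use of the device | 15 + 2 = 17 | 17 |
| It is not use of the device, but target-related events are reported | 2 | 15 + 2 = 17 |
| Only the second 8.2 test is applied, and guided treatment is taken as neither procedure nor device | 2 | 2 |

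The same 17 events give a device-related count of 2 or 17. The third line goes against the first 8.2 sentence, but a site applying the second sentence alone could arrive at it. In no line does the table show that 15 of the events were syncope or hypovolemia.

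**Step 5: do other planned summaries fill the gap?**
- Endpoint 8 (all-cause hospitalization) is not split by cause, and Appendix B sets a minimum stay of 24 hours.
- Endpoint 9 pools worsening heart failure, volume management and medication management, so overload and depletion are not separated. An episode handled remotely or first noted at a scheduled visit does not enter it.
- Endpoint 10 looks at unscheduled hospitalizations by PA-pressure subgroup, but at no adverse events.

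**Step 6: the renal item.** The list is introduced as potential harms of managing to target, yet this item reads "Renal Dysfunction secondary to heart failure". The Appendix B definition has no cause restriction. Renal dysfunction from volume depletion would fit the definition but not the label, and would go to the catch-all.

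**The case against.** The strongest case against is that little is lost. Section 8.2 does require target-related events on a CRF, names the categories and has a catch-all for them. Appendix B defines most of the categories. A table by category could therefore be produced later without new data. The study also does not collect all adverse events. Only those related to a device, a study procedure or treating to target are reportable, so what remains after removing device-related events should be largely procedure- or target-related, and not lost in background LVAD morbidity. Drug and pump changes are logged with reasons and could be matched to events by date. The AE CRF is not part of the documents and may already hold an attribution item. Finally, this is a descriptive feasibility study with no success criterion.

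Most of this stands as a limit on the claim. It does not close the gap. The remainder mixes procedure-related with target-related events and syncope with stroke, and 6.1.3 does not say whether its four rows exclude one another. Matching dates is not a causality judgement, and an attribution that was never asked for cannot be reliably recovered afterwards. The plan also states a finer breakdown where it wants one: device malfunction in 6.1.1 is to be reported separately by device and by type.

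On the renal item, the objection is right that no event is lost. The effect is misplacement.

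**Conclusion.** The planned safety output does not show harm from the strategy by event type, and 5.5.2 does not secure attribution to it. None of the nine items in 8.2 has a planned count, and relation to guided management has no row. The two causality tests in 8.2 and the open meaning of device use in Appendix B add to this, because sites may classify the same event differently.

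A reader might go further and infer that adverse events are recorded only by seriousness and device relation, so that strategy harms cannot be seen at all. The documents do not support that. Section 8.2 requires target-related events and named categories to be reported, and the category data could be tabulated. Nor do they support the view that such events would necessarily fall outside the device-related rows, since Appendix B leaves this open.

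The conclusion rests on 6.1.3 being followed as written and on the AE CRF holding no more attribution than 5.5.2 names. If the CRF already records relation to guided management, the remaining change is to the table and the wording. The counts of 15 and 2 are assumed and say nothing about expected frequency. This is a cheap improvement worth making; it does not undermine the study.

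**What to change.** - **6.1.3:** tabulate events and patients by 8.2 category and by attribution (CardioMEMS, HeartMate, PA-pressure-guided management), with events per patient-time over 6 months, the measure that 6.1.1 already uses for rates. Keep seriousness as a cross-classification, and say whether the rows are mutually exclusive.
- **5.5.2 and the AE CRF:** record attribution to guided management (a medication or pump-speed change made to reach the target) as an item separate from relation to each device.
- **8.2:** use one causality test that names treating to target alongside devices and study procedures. With the separate attribution item, the table no longer depends on whether guided treatment counts as use of the device.
- **8.2 and Appendix B:** reconcile the renal label with the definition, for example by dropping the cause from the label and recording the attributed cause.

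The cost is one more causality judgement per event and one additional table. No visit or test is added.

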6.2 OVERALL SAMPLE SIZE

The sample size of 100 subjects is expected to provide enough data to address each of objectives stated above. This study will inform the design of future clinical studies.

6.3 TIMING OF ANALYSIS

Analyses will be performed when the last patient enrolled completes 6 months of follow-up in the study.

6.4 SUCCESS CRITERIA

As a feasibility study, there are no pre-specified statistical criteria for success.

6.5 INTERIM ANALYSIS

Interim analyses will be conducted as data accumulates in this study. As there are no hypotheses to be tested, type I error control is not applicable.

6.6 STATISTICAL CRITERIA FOR TERMINATION

There are no statistical criteria for termination of this trial.

7 RISKS AND BENEFITS

It is not anticipated that patients would experience any new risks not identified in the User Manual for either the CardioMEMS sensor and the HeartMate LVAS. There are some minor possible risks to the protocol and are listed below. The additional tests and assessments required by the clinical investigation were analyzed for additional risks and are incorporated in the sections below.

7.1 RISKS ASSOCIATED WITH CLINICAL INVESTIGATION ASSESSMENTS

The risks for the CardioMEMS™ device are known and are detailed in the user manuals. No additional risks are known that involve participation in the clinical investigation. If new risks are learned during the course of the study, sites will be notified.

7.2 RISK CONTROL MEASURES

Every possible effort will be taken to minimize the risks, including:

- Careful selection of experienced Investigators for the clinical investigation
- Adequate monitoring for each clinical investigation site
- Conducting the clinical investigation in accordance with the CIP, all applicable laws and regulations and any conditions of approval imposed by the appropriate IRB/EC or applicable regulatory authorities where the clinical investigation is performed
- Use of the HeartMate and CardioMEMS devices and performance will be in accordance with the device IFUs
- Training of Investigators on the CIP

This confidential document is the property of Abbott and shall not be reproduced, distributed, disclosed or used without the express written consent of Abbott.

7.3 ANTICIPATED BENEFITS

The combined use of HeartMate with CardioMEMS has the potential benefit of improving management of HeartMate patients, improving functional status and reducing adverse events and hospitalizations.

7.4 RISK-TO-BENEFIT RATIONALE

The patients enrolled in this study will already have market approved devices implanted on indication for the management of heart failure. Clinicians will be expected to manage the patients per standard of care while data is collected. While no benefit may be found, it is possible that patients will experience reduction in symptoms leading to reduction in frequency of hospitalization for heart failure. This feasibility study is intended to provide data that will be used to inform the design of future clinical studies to answer the question of combined benefit. As such, the benefit outweighs risks supporting the feasibility study.

8 REQUIREMENTS FOR INVESTIGATOR RECORDS AND REPORTS

8.1 DEVIATIONS FROM CIP

A deviation is defined as an instance(s) of failure to follow, intentionally or unintentionally, the requirements of the CIP. The investigator should not deviate from the CIP.

In some cases, failure to comply with the CIP may be considered failure to protect the rights, safety and well-being of subjects; such non-compliance exposes subjects to unreasonable risks. Examples: failure to adhere to the inclusion/exclusion criteria, failure to perform safety assessments intended to detect adverse events. Investigators should seek to minimize such risks by adhering to the CIP.

The PI must maintain accurate, complete, and current records, including documents showing the date of and reason for each deviation from the CIP. Relevant information for each deviation will be documented as soon as possible on the applicable CRF. The site will submit the CRF to the Sponsor.

The PI is required to adhere to local regulatory requirements for reporting deviations to IRB.

An investigator shall notify the Sponsor and the reviewing IRB of any deviation from the investigational plan to protect the life or physical well-being of a subject in an emergency. Such notice shall be given as soon as possible, but in no event later than 5 working days after the emergency occurred. Except in such an emergency, prior approval by the Sponsor is required for changes in or deviations from a plan, and if these changes or deviations may affect the scientific soundness of the plan or the rights, safety, or welfare of human subjects, FDA and IRB is also required.

8.2 SAFETY REPORTING

Safety surveillance within this study and the safety reporting performed both by the investigator and Sponsor for these market release devices starts after the indicated devices have been implanted and as soon as the subject is enrolled in this clinical investigation (refer to section 5.4 for enrollment timing). Procedure related adverse events, prior to both devices being successfully implanted, do not require reporting within this study.

The safety surveillance and the safety reporting will continue until the last investigational visit (six months) has been performed, the subject is deceased, the subject/investigator concludes his participation into the clinical investigation or the subject withdrawal from the clinical investigation.

For purposes of this study, any adverse event that is possibly or likely related to either device, will be collected throughout the clinical investigation. Refer to device specific user manuals. Additionally, adverse events that are possibly or likely related to treating to target ranges (detailed below) will be reported to the Sponsor on a CRF.

Adverse events will be monitored until they are adequately resolved or the subject has ended his/her participation in the trial, whichever comes first. The status of the subject's condition should be documented at each visit.

For the purposes of this clinical investigation, the following events that could be potentially caused by using the CardioMEMS™ device to manage PA pressures to target ranges in patients with HeartMate™ Left Assist devices require reporting. The following adverse events will be required to be reported within the study if they are possibly or likely related to the study procedures or to either of the study devices (see Appendix B for definitions):

- Cardiac Arrhythmias
 - Ventricular Arrhythmia
 - Supraventricular Arrhythmia
 - Both (Ventricular and Supraventricular Arrhythmia)
- Strokes regardless of their types and etiology
 - Hemorrhagic Stroke
 - Ischemic Stroke
 - Debilitating Stroke
- Other Neurological Events felt to be related to managing PA pressures
- Renal Dysfunction secondary to heart failure
- Respiratory Failure secondary to cardiovascular cause
- Right Heart Failure
- Syncope/presyncope/dizziness and hypovolemia
- Worsening Heart Failure
- Other Adverse Event that in the opinion of the investigator are suspected to be related to using the CardioMEMS device to manage PA pressures to target ranges.

All above study defined reportable events will be reported to the Sponsor, as soon as possible, but no later than 3 calendar days of first learning of the event. The Sponsor will ensure that all applicable events are reported to the relevant authorities as per regulations. The sites should notify the Sponsor of reportable adverse events by creating and saving the appropriate adverse event CRF within the electronic data capture (EDC) system. Additional information may be requested by the Sponsor in order to support the reporting of AEs to regulatory authorities. Device issues unrelated to this study, which do not meet the AE requirements by this CIP but fall under complaint definition, will be reported by investigators to Sponsor as complaints through the regular complaint reporting procedure. The investigator must notify the IRB, if appropriate, in accordance with national and local laws and regulations, of the AEs reported to the Sponsor.

8.2.1 Subject Death

All deaths that occur during the investigation, regardless of cause are to be reported to the sponsor. Subject deaths will be documented and reported to the Sponsor as soon as possible, but no later than 3 calendar days after becoming aware of the event via the applicable CRF.

8.2.2 Complaint

A complaint is defined as an inadequacy of a medical device with respect to its identity, quality, durability, reliability, safety or performance. Complaints may be submitted from the time of consent through the end of the study.

If a complaint involves an adverse event category or death as described in the protocol (section 8.2), then the investigator shall notify the Sponsor by completing the adverse event or death case report form as applicable and must provide the Sponsor with all necessary documentation needed.

If the complaint does not involve a reportable adverse event per protocol the investigator should notify the Abbott Product Surveillance Department through one of the methods listed below as soon as possible after becoming aware of a complaint.

CardioMEMS™ related complaints:

Email address: [contact]

Toll Free: [contact]

Direct: [contact]

[contact]

HeartMate™ pump related complaints:

Email address: [contact]

Toll Free: [contact]

Complaints will be collected and reported by Abbott according to our product reporting process

8.3 SOURCE RECORDS

Source documents will be created and maintained by the investigational site team throughout the clinical investigation. The data reported on the CRFs will be derived from, and be consistent with, these source documents, and any discrepancies will be explained in writing. Additionally, sites are required to provide all relevant medical records for adverse events, ER visits, short stays or hospital admissions as requested by the sponsor.

8.4 RECORDS RETENTION

The Sponsor and the Principal Investigators will maintain the clinical investigation documents as required. Measures will be taken to prevent accidental or premature destruction of these documents. The Principal Investigator or the Sponsor may transfer custody of records to another person/party and document the transfer at the investigational site or the Sponsor's facility, as appropriate.

These documents must be retained by the investigational site for a period of 2 years after the conclusion of the clinical investigation and made available for monitoring or auditing by the Sponsor's representative or representatives of the applicable regulatory agencies.

All original source documents must be stored for the maximum time required by the regulations at the hospital, research institute, or practice in question. If original source documents can no longer be maintained at the site, the investigator will notify the Sponsor.

